		4.12.13 Laboratory Results	
5	REFI	FRENCES	31

REVISION HISTORY

Version	Date	Reason for Revision
1.0	15AUG2017	Incorporated sponsor's comments and changed in the new protocol dated August 12, 2017
		Notable changes per comments:
		added definition of sub-study analysis population
		switched names of relevant and evaluable cycles
		reduced number AE tables for ITT population
		dropped nonparametric analysis for Likert pain score in the sub-study
2.0	17NOV2017	Incorporate protocol version 2.0
3.0	25JUNE2018	Incorporate protocol version 3.0; remove the randomized arm; add 7-day lockout for diary entries, follow-up for 6 weeks post-delivery for any ontreatment pregnancies, added serum pregnancy test for all suspected pregnancies

LIST OF ABBREVIATIONS AND DEFINITIONS OF TERMS

AΕ adverse event

AESI adverse event of special interest

BMI body mass index CRF case report form

DSMB data and safety monitoring board

eCRF electronic case report form **ECYC** evaluable for cycle control EP evaluable for pregnancy

International Council for Harmonization **ICH**

ITT intent to treat

IUD intrauterine device

MedDRA Medical Dictionary for Regulatory Activities

PID pelvic inflammatory disease

PT preferred term

SAE serious adverse event SAP statistical analysis plan SOC

system organ class

TEAE treatment-emergent adverse event

US **United States**

1 INTRODUCTION

This document presents the planned statistical analyses for Sebela Pharmaceuticals Development LLC (Sebela) study titled "A Phase 3, Prospective, Multi-Center, Single-Arm, Open-Label Study to Evaluate VeraCept™, a Long-Acting Reversible Intrauterine Contraceptive for Contraceptive Efficacy, Safety, and Tolerability," protocol number CMDOC-0042, version 3.0, dated June 15, 2018. The statistical analysis plan (SAP) summarizes key aspects of the study rationale and design to provide context for the statistical methods. It also presents details of the planned statistical methods addressing the study aims. The statistical principles applied in the design and planned analyses of this study are consistent with the International Council for Harmonization (ICH) guidelines E9 (Statistical Principles for Clinical Trials).

Sebela or its designee, will write the clinical study report (CSR) following the guidelines in the ICH E3 document.

1.1 Background of VeraCept

The VeraCept Intrauterine Contraceptive ("VeraCept") is designed as a hormone free, low dose, copper-releasing birth control method. In the United States, there are over 62 million women in their child-bearing years, ages 15 to 44. Thirty-eight million of these women (62%) use some form of contraception. Thirty-one percent (31%) do not use or need contraception because they are either trying to get pregnant, are pregnant, are infertile, or are not sexually active. Seven percent (7%) are at risk for unintended pregnancy because they are not using any contraceptive method [1].

Contraceptive options for the 38 million US women using contraception include permanent sterilization (tubal ligation or vasectomy in male partner), contraceptive implants, intrauterine devices (IUDs), injections, pills, patches, vaginal rings, male and female condoms, other female barrier methods, vaginal spermicides, and behavioral methods such as coitus interruptus and fertility awareness. Of all these methods, oral contraceptives are used by 30% of sexually active women. The more effective methods, such as intrauterine contraceptives, are used by fewer than 10% of women [2]. The CHOICE Study showed that the pill failure rate is 20 times higher than the failure rate with IUDs [3,4].

Intrauterine devices have high initial costs, and therefore early discontinuation rates have a profound impact on their cost effectiveness. The early rates of user dissatisfaction due to complications or side effects may be associated with the materials used and/or their design. The ParaGard® Copper T380 IUD has been associated with complaints of increased bleeding, intermenstrual bleeding, and cramping pain. The LNG-IUS (Mirena®) is also associated with early complaints of irregular bleeding patterns, cramping pelvic pain, and amenorrhea. First year discontinuation rates for copper IUDs in most studies range from 4%-15% [5,6,7].

With high unintended pregnancy rates in the United States (49%) [1], additional effective, safe, and long-acting reversible contraceptives are needed. An IUD with low-dose copper that achieves high contraceptive effectiveness, minimizes side effects, and has improved mechanical advantages could offer an attractive option to women seeking effective protection against unintended pregnancy. We believe VeraCept embodies these advantages.

The favorable safety, tolerability, and effectiveness data observed at 24-months in the Phase 2 study support initiation of this Phase 3 clinical trial for VeraCept.

2 STUDY OBJECTIVES AND ENDPOINTS

2.1 Objectives

The primary objective of the study is to assess the contraceptive efficacy (prevention of pregnancy) of VeraCept.

The secondary objectives of the study are to assess the following for VeraCept:

- Safety and tolerability
- Return to fertility after VeraCept removal, only for subjects requesting VeraCept removal to become pregnant

2.2 Endpoints

The primary endpoint is the contraceptive efficacy through 3 years of use, as assessed by the Pearl Index. The Pearl Index will be calculated for Years 1, 2, and 3 as well as cumulatively through Year 3.

Secondary endpoints include:

Contraceptive efficacy

- Pearl Index at Years 4 and 5 as well as cumulatively through Years 4 and 5
- Pregnancy percentage by life table analysis (Kaplan Meier) at Years 1, 2, 3, 4, and 5

Study drug placement

- Ease of placement
- Placement success

Safety

- Serious adverse events (SAEs)
- Adverse events (AEs)
- Pelvic infection (pelvic inflammatory disease [PID] or endometritis)
- Ectopic pregnancies
- Uterine perforations
- Dysmenorrhea
- Abdominal Pain
- Expulsion rates at Years 1, 2, 3, 4, and 5

Tolerability

- Bleeding and spotting patterns
- Insertion pain assessed immediately after insertion
- Continuation rates at Years 1, 2, 3, 4, and 5

• Reasons for discontinuation

Return to fertility

 Pregnancy rate in subjects who wish to become pregnant after VeraCept removal specifically to become pregnant. Subjects who desire pregnancy after having VeraCept removed will be followed for either 1 year, until they decide to no longer try to conceive or they become pregnant, whichever comes first.

3 STUDY DESIGN AND INVESTIGATIONAL PLAN

This study is a prospective, multi-center, single-arm, open-label, Phase 3 clinical study to 3 years with an extension up to 5 years.

3.1 Study Population

Post-menarcheal, pre-menopausal women up to age 45 years, who are at risk for pregnancy and who desire a long-term intrauterine contraceptive for birth control will be eligible for this study. Both parous and nulliparous women are eligible. Subjects must provide written informed consent and assent, if applicable, and meet the study subject selection criteria without any exclusions, as outlined in the Clinical Investigation Plan.

3.2 Study Duration

Subject enrollment will take approximately 9 months. Subjects will be followed for up to 5 years after VeraCept placement. Women requesting VeraCept removal for a desired pregnancy will be followed for up to 1 year after the IUD is removed. The total study duration for a subject being followed for return to fertility could be up to 6 years. Any on-treatment pregnancies will be followed through delivery and for at least 6 weeks post-delivery.

3.3 Number of Subjects

Approximately 1,605 subjects will be enrolled into this study to receive VeraCept on an open-label basis. It is planned that approximately 1,480 of the 1,605 subjects will be up to 35 years of age, and the remaining 125 subjects will be in the 36- to 45-year age range.

3.4 Investigational Sites

This study will be conducted at approximately 45 centers in the United States.

3.5 Follow-up

Subjects will have physical assessments (office visits) at Weeks 6, 13, 26, and 52 in Year 1, and then every 6 months for up to 5 years after VeraCept placement. Regular follow-up contact visits will be conducted monthly starting at Week 17, except when there is a scheduled office visit, through Year 3. For Years 3 to 5, additional visits will be conducted if necessary for safety issues.

Follow-up after early study drug removal:

All subjects who have the IUD removed while on the study, for any reason, will be required to use an alternative contraceptive for the first 2 weeks following removal. Hormonal contraceptive pills and emergency contraception will be reimbursed by the sponsor as a contraceptive option during this time unless the subject has a medical condition precluding their use.

Follow-up for subjects desiring pregnancy:

Subjects requesting VeraCept removal to become pregnant will be followed for 1 year, until they decide to no longer try to conceive or they become pregnant, whichever comes first.

Follow-up for on-treatment pregnancy subjects:

Any on-treatment pregnancies will be followed through delivery and for at least 6 weeks post-delivery. Any infant abnormalities should be reported.

3.6 Study Schedule of Assessments

A schedule of assessments is provided in Table 1.

3.7 Determination of Sample Size

Approximately 1,605 subjects will be enrolled into this study to receive VeraCept on an open-label basis. It is planned that 1,480 of the 1,605 subjects will be in the up to 35-year age range and the remaining 125 subjects will be in the 36- to 45-year age range. It is expected that at least 40% of enrolled subjects will be nulliparous.

It is expected that 1,480 post-menarcheal subjects up to age 35 years will provide at least 620 women with at least 3 years of use of VeraCept. It is expected that the study will have 577 woman-years of use in Year 3 of the study that are evaluable for the Pearl Index analysis. This will allow for the Pearl Index calculation for Years 1, 2, and 3 of the study and for the cumulative 3 years to have an upper bound of the 95% CI no more than 1 unit above the point estimate of the Pearl Index.

It is also expected that 1,480 post-menarcheal VeraCept subjects up to age 35 years will provide at least 350 women with 5 years of use of VeraCept.

The 1,605 enrolled VeraCept subjects are expected to provide over 17,000 cycles (28-day cycles) of exposure in Year 1. Over 54,000 VeraCept cycles are expected to be collected during the course of the 5-year study.

3.8 Interim Analyses

The Sponsor may review the primary and secondary endpoints for the study after 200 subjects have completed 3 years of treatment to assess if the data supports the filing of an NDA for approval of an indication with 3 years of use.

3.9 Data and Safety Monitoring Board

The study will utilize a data and safety monitoring board (DSMB) to oversee safety and performance outcomes (stopping rules will be further defined in the DSMB charter).

The stopping criteria will be assessed by observing the lower bound of the 95% CI of the cumulative pregnancy percentage (Kaplan-Meier) at the given time point (e.g., Cycle 6) for the VeraCept treatment. If the lower bound of the 95% CI is greater than the decision point for the given DSMB meeting, then the DSMB will recommend suspension of enrollment into the study until a thorough review of risks and benefits can be performed since subjects appear to be at a higher risk of pregnancy than expected. The decision point used for each DSMB meeting will depend upon how much data is expected to be available at the time point of interest (e.g., Cycle 6) for the DSMB meeting. The time point used for the Kaplan-Meier analysis and the

decision point for each DSMB meeting will be specified in the DSMB charter. The DSMB charter will detail the number and timing of DSMB reviews. The sponsor can request additional DSMB meetings if they have any concerns.

4 STATISTICAL METHODOLOGY AND ANALYSIS

4.1 Definitions and Derivations

4.1.1 Standard Calculations

Variable	Calculation			
Age (Years) at Informed Consent	Floor [Date of informed consent – date of birth+1) /365.25]			
Height	Height entries made in inches (in) are converted to centimeters (cm) using the following formula: height (cm) = height (in) * 2.54			
Weight	Weight entries made in pounds (lb) are converted to kilograms (kg) using the following formula: weight (kg) = weight (lb) / 2.2046			
Temperature	Temperature entries in degrees Fahrenheit are converted to degrees centigrade using the following formula: temp (degrees centigrade) = 5/9 * [temp (degrees Fahrenheit) - 32]			
Body Mass Index (BMI)	BMI is calculated using height (cm) and weight (kg) using the following formula: BMI (kg/m ²) = weight (kg) / [[height (cm)/100] ²]			

4.1.2 Reference Date and Study Day Calculation

A subject could have 2 study drug insertion attempts, which could be on different dates. The following 2 study reference dates will be defined to meet the analysis requirement specified in the protocol and this SAP.

- First study reference date=date of the first insertion attempt
- Second study reference date=date of successful insertion

The first study reference date will be used for Intent-to-Treat (ITT) analysis to include all data since first device insertion attempt regardless of insertion success or failure (e.g., AEs related to replacement procedure).

The second study reference date will be used to define exposure period and analysis visit windows for all cycle-based analysis and analysis for data with scheduled data collection.

The second study reference date is Day 1 of Cycle 1.

For both reference dates, study day will be calculated as follows:

If event date > study reference date:

Study day of event = Event date - Study reference date + 1

If event date < study reference date:

Study day of event = Event date – Study reference date

4.1.3 Baseline and Change from Baseline

Baseline is defined as last non-missing observation before or on date of successful insertion

- Change from baseline (CHG)= post-baseline value baseline
- Percent change from baseline =100.0×CHG/Baseline

4.1.4 Analysis Windows

For analysis purpose, early termination visits and unscheduled follow-up visits will be assigned analysis visits according to the analysis windows in the following table. This mapping applies to labs, vital signs, and all other data planned to be collected and analyzed by visit in the SDTM finding domains. Where multiple measurements for a particular parameter appear within an analysis window the result closest to target day will be used. If equidistant, the later result will be used for the summary measure. Though all measures may not be used in the data summaries (e.g., 2 lab measures within the same analysis visit window), all measurements appear in the datasets and listings.

Analysis windows:

		Analyzia	Analysis Window			
Scheduled Visit	Analysis	Analysis Window	Lower	Upper		
(Subject Visit Window)	Visit	Target Day	Bound	Bound		
Visit 1/Screening						
Visit 2 (Day 1)	Baseline	1		1		
Visit 3 (Week 6±1 week)	Week 6	42	2	67		
Visit 4 (Week 13±2 weeks)	Week 13	91	68	137		
Visit 5 (Week 26±2 weeks)	Week 26	182	138	273		
Visit 6 (Week 52±2 weeks)	Week 52	364	274	456		
Visit 8 (Month 18± 1 month)	Month 18	548	457	639		
Visit 9 (Month 24± 1 month)	Month 24	730	640	822		
Visit 10 (Month 30± 1 month)	Month 30	913	823	1004		
Visit 12 (Month 36± 1 month)	Month 36	1095	1005	1187		
Visit 13 (Month 42± 1 month)	Month 42	1278	1188	1369		
Visit 14 (Month 48± 1 month)	Month 48	1460	1370	1551		
Visit 15 (Month 54± 1 month)	Month 54	1643	1552	1734		
Visit 16 (Month 60± 1 month)	Month 60	1825	1735	≥1735		

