12.10 Unscheduled Visits

Unscheduled visits will be documented in the source and the CRFs. Medical evaluations will be conducted as indicated by the reason for the unscheduled visit.

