4.12.11 Vital Signs and Weight

The observed values and changes from baseline in the following vital signs and weight parameters will be summarized by visit for the Safety population:

- Systolic blood pressure (mm Hg)
- Diastolic blood pressure (mm Hg)

- Pulse rate (bpm) sitting
- Respiration rate (breaths/min)
- Body temperature
- Body weight (kg)

The number and percentage of patients reporting potentially clinically meaningful observations as defined below will be summarized by visit and treatment group:

- Systolic blood pressure: $\leq 80 \text{ mm Hg or } \geq 140 \text{ mm Hg}$
- Diastolic blood pressure: $\leq 40 \text{ mm Hg or } \geq 90 \text{ mm Hg}$
- Pulse rate: ≤ 50 bpm or ≥ 100 bpm
- Respiration rate: < 8 or > 20 breaths/min

Vital signs and weight will be included in data listings.

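### By-visit counts of abnormal vital signs use one reading per analysis window, so many early-exit readings and most unscheduled ones would not be counted; an any-post-baseline row would close the gap

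*SAP*

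**What the plan says.** SAP 4.1.4 states that "early termination visits and unscheduled follow-up visits will be assigned analysis visits according to the analysis windows in the following table". On scope it says "This mapping applies to labs, vital signs, and all other data planned to be collected and analyzed by visit in the SDTM finding domains". Within a window, "Where multiple measurements for a particular parameter appear within an analysis window the result closest to target day will be used", and for ties "If equidistant, the later result will be used for the summary measure". The same section openly says that unused values appear only in the datasets and listings.

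SAP 4.12.11 applies fixed limits to blood pressure, pulse and respiration rate (for example systolic pressure at or below 80 mm Hg, pulse at or above 100 bpm): "The number and percentage of patients reporting potentially clinically meaningful observations as defined below will be summarized by visit and treatment group". It plans no worst-value or any-time row and does not exempt these counts from the selection rule.

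The protocol requires vital signs at the exit visit (12.7). That visit is to be completed on early discontinuation for an adverse event, for a desired pregnancy or after expulsion (12.9.1 to 12.9.3). At other extra visits vital signs are not mandatory: "Medical evaluations will be conducted as indicated by the reason for the unscheduled visit" (12.10).

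**The concern.** Choosing the reading closest to target suits means and changes from baseline, where each woman should contribute one comparable value per time point. A threshold count asks a different question: did she have a reading beyond the limit? For that purpose the rule sets readings aside by date alone.

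Take a hypothetical case in the Month 18 window (days 457-639, target 548). A woman attends her scheduled visit on day 560, 12 days from target, and has the device removed on day 610, 62 days from target. Her exit vital signs are collected as the protocol requires, yet the day 560 reading represents her in the table whatever the exit reading showed.

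What is at stake is the completeness of the planned tabulation of threshold abnormalities in vital signs, the one that does not depend on an investigator's judgement of clinical significance. The primary endpoint is not affected.

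**Working it through.** **Reproducing the plan's windows.** Each upper bound should be the midpoint between neighbouring target days. From Week 6 to Month 54 the midpoints are 66.5, 136.5, 273, 456, 639, 821.5, 1004, 1186.5, 1369, 1551.5 and 1734. The stated bounds are 67, 137, 273, 456, 639, 822, 1004, 1187, 1369, 1551 and 1734. All 11 agree within half a day. Each of these windows holds one scheduled office visit. The monthly contacts take no vital signs.

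**Assumptions (not in the documents).** The scheduled visit is attended and falls with equal chance on any day within ±h of the target *t*, with h = 7 for Weeks 6 and 13 (the schedule of assessments in both documents; the SAP window table prints ±2 weeks for Week 13), 14 for Weeks 26 and 52, and 30 for the monthly-labelled visits. The extra or exit visit falls with equal chance on any of the N days of the analysis window.

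**Unscheduled reading.** It is kept if it is closer to target, if it ties and is later, or if it falls on the same day. Averaging over the 2h+1 scheduled days, the number of days on which it is kept is h+1. Share dropped = 1 − (h+1)/N.

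**Exit reading.** If exit comes before the scheduled visit, the exit reading is the only one in the window and is kept. It is dropped only if the scheduled visit came first and was closer, which means the exit lies beyond *t* by more than the scheduled visit's distance. The mean distance is h(h+1)/(2h+1): 3.73 for h = 7, 7.24 for h = 14 and 15.25 for h = 30. Share dropped = (upper bound − *t* − mean distance)/N.

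| Window | N | Unscheduled dropped | Exit dropped |
|---|---|---|---|
| Week 6 | 66 | 1 − 8/66 = 88% | (67−42−3.73)/66 = 32% |
| Week 13 | 70 | 1 − 8/70 = 89% | (137−91−3.73)/70 = 60% |
| Week 26 | 136 | 1 − 15/136 = 89% | (273−182−7.24)/136 = 62% |
| Week 52 | 183 | 1 − 15/183 = 92% | (456−364−7.24)/183 = 46% |
| Months 18-54 | 182-183 | 1 − 31/183 = 83% | e.g. Month 18: (639−548−15.25)/183 = 41%; others 41-42% |

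**Pooled by window length.** To Month 36 there are 1,186 days. Unscheduled dropped: 1 − 170/1,186 = 86%. Exit dropped: 537.1/1,186 = 45%. To Month 54 (1,733 days) the figures are 85% and 44%. The Month 60 window has no upper bound and is left out.

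**Sensitivity (all assumed).**

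- Exits concentrated early (decline of 0.2 to 0.5 per year): exit 45-47%.
- 20% of scheduled visits missed: unscheduled about 68%, exit 35-38%.
- 10% to 30% of scheduled visits late, spread up to the opening of the next visit window (to Month 36): unscheduled 79% down to 65%, exit 42% down to 35%.
- As the previous line, with 25% of exits coinciding with the scheduled visit: exit 31% down to 26%.
- Scheduled visits exactly on target: unscheduled 99%, exit about 52%.

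**The case against.** The strongest reply is that the clinically important cases reach the report by another route. Protocol 15.8 names vital signs among the abnormal assessments that must be recorded as adverse events when they come with symptoms or need treatment, and as serious ones if they meet those criteria. The tables in SAP 4.12.1 and 4.12.2 are not subject to closest-to-target selection. This stands, and it narrows the point considerably.

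A reader might infer that the rule would hide haemorrhage or sepsis, which Protocol 6.2 lists as risks. The documents do not support that. Such events would be recorded as adverse events, and SAP 4.12.11 sets no temperature limit, so the table is a weak screen for sepsis under any selection rule.

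A reader might also infer that the table is tilted towards normal values. Selection is by date and ignores the value. A tilt would need abnormal readings to be more frequent at extra visits. That is plausible for visits prompted by a complaint, but exits for a desired pregnancy or after expulsion have no evident link to abnormal vital signs, and the documents give no abnormality rates.

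A headcount is tempting too. Applying 1 − 620/1,480 = 58% to 1,605 women gives about 933 early leavers, and 45% of these, with 70-100% having an exit visit, gives about 290-420 readings. That is an upper-end figure. The sample size section says at least 620, the ratio applies to women up to 35, and 1,605 includes failed placements, whereas this summary uses the Safety population. Losses to follow-up also make complete exit visits unlikely. Each woman affected still contributes a reading in that window.

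Finally, the rule is disclosed, vital signs are not a study endpoint, and the protocol's safety analysis section plans no vital-sign summary. These are fair reasons to treat the change as optional.

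**Conclusion.** The point holds as a limited gap in one safety table. As written, the rule omits about 45% of early-exit readings from the abnormality counts under the main timing assumptions, and roughly 25-50% over the variations tried. It omits most unscheduled readings (65% to 99%). These are shares under assumed visit timing. How many unscheduled readings will exist is unknown and may be small, and the change in the reported percentages cannot be computed. What is lost from the summary is mainly threshold crossings that no investigator judged clinically significant, and those remain in the listings.

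**What to change.** Keep the closest-to-target rule in SAP 4.1.4 for observed values, changes from baseline and the by-visit counts. Add to SAP 4.12.11 one row per criterion giving the number and percentage of women with any post-baseline reading, whether scheduled, unscheduled or at exit, that meets it. In that row no reading is dropped.

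This takes a sentence of SAP text and minor programming, with no new data. The costs are slightly higher reported percentages and the fact that women with more visits have more chances to be flagged, which a table footnote should state.
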